2. STUDY OBJECTIVES AND ENDPOINTS

2.1 Study Objectives

2.1.1 Primary Objective

• To demonstrate the efficacy of SARS-CoV-2 rS with Matrix-M1 adjuvant in the prevention of virologically confirmed (by polymerase chain reaction [PCR] to SARS-CoV-2), symptomatic COVID-19, when given as a 2-dose vaccination regimen, as compared to placebo, in serologically negative (to SARS-CoV-2) adult participants.

2.1.2 Secondary Objectives

- To demonstrate the efficacy of SARS-CoV-2 rS with Matrix-M1 adjuvant in the prevention of virologically confirmed (by PCR to SARS-CoV-2), symptomatic COVID-19, when given as a 2-dose vaccination regimen, as compared to placebo, in adult participants regardless of their serostatus at baseline.
- To assess the efficacy of SARS-CoV-2 rS with Matrix-M1 adjuvant on SARS-CoV-2 seropositive adult participants requiring specific medical interventions as compared to placebo.
- To assess the efficacy of SARS-CoV-2 rS with Matrix-M1 adjuvant on mild COVID-19 symptoms as compared to placebo.
- To assess the efficacy of SARS-CoV-2 rS with Matrix-M1 adjuvant on occurrence of asymptomatic or undetected infections with SARS-CoV-2 as compared to placebo.
- In a subset of adult participants, to evaluate the immunogenicity of SARS-CoV-2 rS with Matrix-M1 adjuvant as compared to placebo.
- To evaluate safety in terms of SAEs and medically attended adverse events (MAAEs) related to study vaccination in all adult participants during the entire study period.
- To evaluate safety in terms of AESI, which encompasses potential immune-mediated medical conditions (PIMMCs) and AESIs relevant to COVID-19, including possible vaccine-enhanced disease, in all adult participants at any time after the first dose.
- In a subset of adult participants, to evaluate the safety and reactogenicity in terms of solicited local and systemic adverse events (AEs) for 7 days after each study vaccination.
- To evaluate safety in terms of all MAAEs for 14 days after second vaccination and unsolicited AEs for 21 days after first study vaccination and 28 days after second study vaccination.

2.1.3 Exploratory Objective

• In a subset of adult participants, to evaluate the safety and immunogenicity of SARS-CoV-2 rS with Matrix-M1 adjuvant when co-administered with a licensed seasonal influenza vaccine.

2.2 Study Endpoints

2.2.1 **Primary Endpoints**

• First occurrence of virologically confirmed (by PCR to SARS-CoV-2), symptomatic mild, moderate, or severe COVID-19 (Table 2-1) with onset at least 7 days after second study vaccination (e.g., Day 28) in serologically negative (to SARS-CoV-2) adult participants at baseline until the endpoint-driven efficacy analysis is triggered by the occurrence of a prespecified number of blinded endpoints.

•

 Table 2-1:
 Endpoint Definitions of COVID-19 Severity

COVID-19 Severity	Endpoint Definitions
Mild	 ≥ 1 of: Fever (defined by subjective or objective measure, regardless of use of anti-pyretic medications) New onset cough ≥ 2 COVID-19 respiratory/non-respiratory symptoms in Table 2-2 AND Does not meet criteria for moderate or severe disease
Moderate	 ≥ 1 of: Fever (defined by subjective or objective measure, regardless of use of anti-pyretic medications) + any 2 COVID-19 symptoms in Table 2-2 for ≥ 3 days (need not be contiguous days) High fever (≥ 38.4°C) for ≥ 3 days (need not be contiguous days) Any evidence of significant LRTI: Shortness of breath (or breathlessness or difficulty breathing) with or without exertion (greater than baseline) Tachypnea: 20 to 29 breaths per minute at rest SpO2: 94% to 95% on room air Abnormal chest x-ray or chest CT consistent with pneumonia or LRTI Adventitious sounds on lung auscultation (e.g., crackles/rales, wheeze, rhonchi, pleural rub, stridor) AND Does not meet criteria for severe disease

Table 2-1:	Endpoint Definitions of COVID-19 Severity
------------	---

COVID-19 Severity	Endpoint Definitions
Severe	 ≥ 1 of: Tachypnea: ≥ 30 breaths per minute at rest Resting heart rate ≥ 125 beats per minute SpO₂: ≤ 93% on room air or PAO₂/FiO₂ < 300 High flow oxygen therapy or NIV/NIPPV (e.g., CPAP or BiPAP) Mechanical ventilation or ECMO One or more major organ system dysfunction or failure (e.g., cardiac/circulatory, pulmonary, renal, hepatic, and/or neurological, to be defined by diagnostic testing/clinical syndrome/interventions), including any of the following: ARDS Acute renal failure Acute renal failure Septic or cardiogenic shock (with shock defined as SBP < 90 mm Hg OR DBP < 60 mm Hg Acute stroke (ischemic or hemorrhagic) Acute thrombotic event: AMI, DVT, PE Requirement for: vasopressors, systemic corticosteroids, or hemodialysis. Admission to an ICU Death

Abbreviations: AMI = acute myocardial infarction; ARDS = acute respiratory distress syndrome; BiPAP = bi-level positive airway pressure; CPAP = continuous positive air pressure; CT = computed tomography; DBP = diastolic blood pressure; DVT = deep vein thrombosis; ECMO = extracorporeal membrane oxygenation; FiO₂ = fraction of inspired oxygen; ICU = intensive care unit; LRTI = lower respiratory tract infection; NIV = non-invasive ventilation; NIPPV = non-invasive positive pressure ventilation; PAO₂ = partial pressure of oxygen in the alveolus; PE = pulmonary embolism; SBP = systolic blood pressure; SpO₂ = oxygen saturation.

Table 2-2:Qualifying Symptoms of Suspected COVID-19

- Fever
- New onset cough
- New onset or worsening of shortness of breath or difficulty breathing compared to baseline
- New onset fatigue
- New onset generalised muscle or body aches
- New onset headache lasting \geq 48 hours
- New loss of taste or smell
- Acute onset of sore throat, congestion, and runny nose
- New onset nausea, vomiting, or diarrhea lasting \geq 48 hours
- •

Abbreviations: COVID-19 = coronavirus disease 2019.

2.2.2 Secondary Endpoints

2.2.2.1 Key Secondary Endpoint

• First occurrence of virologically confirmed (by PCR to SARS-CoV-2), symptomatic moderate or severe COVID-19 with onset at least 7 days after second study vaccination (e.g., Day 28) in serologically negative (to SARS-CoV-2) adult participants at baseline until the endpoint-driven efficacy analysis is triggered by the occurrence of a prespecified number of blinded endpoints.

2.2.2.2 Other Secondary Endpoints

- First occurrence of virologically confirmed (by PCR to SARS-CoV-2), symptomatic mild, moderate, or severe COVID-19, with onset at least 7 days after second study vaccination (e.g., Day 28) in adult participants regardless of their serostatus at baseline.
- First occurrence of COVID-19 requiring hospitalisation, intensive care unit (ICU) admission or mechanical ventilation linked to any virologically confirmed (by PCR to SARS-CoV-2) COVID-19 with onset at least 7 days after second study vaccination (e.g., Day 28) in adult participants regardless of their serostatus at baseline.
- First occurrence of virologically confirmed (by PCR to SARS-CoV-2), symptomatic mild COVID-19 (with no progression to moderate or severe COVID-19 during the course of the COVID-19 episode) with onset at least 7 days after second study vaccination (e.g., Day 28) in adult participants regardless of their serostatus at baseline.
- First occurrence of laboratory-confirmed (by PCR or nucleocapsid [N] protein serology to SARS-CoV-2) symptomatic or asymptomatic COVID-19 with onset at least 7 days after second study vaccination (e.g., Day 28) in adult participants regardless of their serostatus at baseline.
- Analysis of antibodies binding to the SARS-CoV-2 spike (S) protein by enzymelinked immunosorbent assay (ELISA) at Day 0 (baseline) and Day 35 (14 days after second study vaccination).
- The occurrence and relationship to study vaccination of SAEs and MAAEs related to study vaccination (in all adult participants) during the entire study period.
- The occurrence and relationship to study vaccination of AESIs and PIMMCs (in all adult participants) during the entire study period.
- The occurrence and severity of reactogenicity in terms of solicited local and systemic AEs (in all sub-study participants) for 7 days after each study vaccination.

• The occurrence, severity, and relationship to study vaccination of all MAAEs for 14 days after second vaccination and unsolicited AEs (in all adult participants) for 21 days after first study vaccination and 28 days after second study vaccination.

2.2.3 Exploratory Endpoints

- First occurrence of virologically confirmed (by PCR to SARS-CoV-2), symptomatic mild, moderate, or severe COVID-19 with onset at least 14 days after first study vaccination (e.g., Day 14) in serologically negative (to SARS-CoV-2) adult participants at baseline until the endpoint-driven efficacy analysis is triggered by the occurrence of a prespecified number of blinded endpoints.
- Any occurrence of serologic conversion (by serology to SARS-CoV-2 N protein) between baseline and 1 year after last study vaccination in adult participants seronegative at baseline.
- Analysis of the proportion of adult participants with evidence of seroconversion as demonstrated by antibodies to the SARS-CoV-2 S protein by ELISA at Day 35 (14 days after second study vaccination).
- Analysis of the cell-mediated immune responses (for example, as measured by enzyme-linked immune absorbent spot (ELISpot) ± intracellular cytokine staining) on Days 0 (baseline) and 35 (14 days after second study vaccination).
- SARS-CoV-2 neutralisation as measured by virus neutralisation assay (VNA; wildtype virus and/or pseudovirion expressing SARS-CoV-2 S protein) at Day 0 (baseline) and Day 35 (14 days after second study vaccination).
- Analysis of the safety and immunogenicity of SARS-CoV-2 rS with Matrix-M1 adjuvant when co-administered with seasonal influenza vaccine in a subset population.

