4.3 Other Considerations

Participants meeting any of the following criteria may have planned study vaccination deferred for a later date, but these criteria are not exclusionary for study enrolment.

- Respiratory symptoms in the past 3 days (i.e., cough, sore throat, difficulty breathing). Participant may be vaccinated once all symptoms have been resolved for > 3 days. Out-of-window study vaccination is allowed for this reason (see NOTE).
- Temperature of > 38°C within 24 hours of planned study vaccination (site measured or participant measured). Participant may be vaccinated once the fever has resolved and there has not been any temperature measured as being > 38°C for > 3 days. Out-of-window study vaccination is allowed for this reason (see NOTE).

NOTE: PCR testing for SARS-CoV-2 is likely to be indicated for either of the above reasons or if COVID-19 is suspected based on other symptoms, potential exposure to SARS-CoV-2 infection through either close contacts or based on local epidemiology. If a participant has a positive PCR for SARS-CoV-2 prior to enrolment that participant will not be eligible and will be considered a screen failure.

- Participants having any symptoms or signs of possible COVID-19 infection (Table 2-2) that may also be due to post-vaccination reactogenicity within 7 days of either study vaccine dose will NOT be required to be tested for SARS-CoV-2 PCR.
- Any participant with a new positive PCR-confirmed SARS-CoV-2 infection occurring from Screening and prior to second study vaccination will not be removed from the study but must meet health requirements before receiving the second study vaccination.
- Any participant who has a positive PCR for SARS-CoV-2 between the first and second study vaccination should also have PCR testing for SARS-CoV-2 on the day of the subsequent study vaccination, but the results of the PCR test are not needed before study vaccination can be given.
- Any participant with a new positive PCR-confirmed SARS-CoV-2 infection occurring from Screening and prior to the end of immunogenicity assessments will be removed from applicable immunogenicity analyses as defined in the SAP.

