6.2.2 Virologic Confirmation of SARS-CoV-2

Nose/throat sampling will be performed to virologically confirm (by PCR to SARS-CoV-2) the presence of SARS-CoV-2 beginning on Day 0 until the EOS, yet only those SARS-CoV-2 cases detected 7 days after second study vaccination will be utilised in study efficacy endpoints.

If a participant experiences any symptom in Table 2-2, this will trigger:

- Nose/throat self-sampling once daily for 3 consecutive days. If any test is found to be positive before 3 consecutive days of testing is performed, the full 3 consecutive tests may not be required. Participants will self-sample based on the training given on Day 0.
- Nose/throat sampling will be started approximately 24 hours after the first symptom(s) from Table 2-2 are reported.

The logistics and processing of these samples is being coordinated by the Department of Health and Social Care (DHSC) (UK government) as part of the national community testing programme.

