7.2 Analysis Sets

The all-randomised set will include all participants who were randomised regardless of the receipt of any study vaccine (SARS-CoV-2 rS with Matrix-M1 adjuvant or placebo). The all randomised set will be used for the subject disposition summaries.

SARS-CoV-2 rS Vaccine Novavax, Inc. Confidential Version 2.0 – 23 October 2020

The intent-to-treat (ITT) analysis set will include all participants who are randomised and receive at least 1 dose study vaccine (SARS-CoV-2 rS with Matrix-M1 adjuvant or placebo), regardless of protocol violations or missing data. The ITT analysis set will be used as a supportive analysis population for the immunogenicity and efficacy analyses and will be analysed according to the study vaccine group as randomised.

The safety analysis set will include all participants who receive at least 1 dose of study vaccine (SARS-CoV-2 rS with Matrix-M1 adjuvant or placebo). Participants in the safety analysis set will be analysed according to the study vaccine actually received.

The PP-EFF will include baseline seronegative participants who receive both doses of study vaccine (SARS-CoV-2 rS with Matrix-M1 adjuvant or placebo) and have no major protocol deviations that occur before the first COVID-19 episode affecting the primary efficacy outcome as assessed by the sponsor prior to unblinding. All analyses of the PP-EFF population will also exclude any illness episodes with positive SARS-CoV-2 by any validated PCR or antibody test occurring before 7 days after second study vaccination (e.g., Day 28).

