7.3.1 Efficacy Analyses

The primary endpoint will be analysed on the PP-EFF Analysis Set and supported by analysis of the ITT Analysis Set. Conclusions concerning declaration of attainment of the primary endpoint at the completion of the study will only be based on the PP-EFF population.

VE is defined as VE $(\%) = (1 - RR) \times 100$, where RR = relative risk of incidence rates between the 2 study vaccine groups (SARS-CoV-2 rS with Matrix-M1 adjuvant or placebo). The final analysis for the primary objective in the PP-EFF population will be carried out at the overall one-sided Type I error rate of 0.025 for the 3 planned analyses. The nominal alpha to be spent for the final analysis will be recalculated using the Lan-DeMets alpha spending function based on the actual numbers of events used for the interim analyses and the numbers of endpoints to be used for the final analysis. The estimated RR and its CI will be derived using Poisson regression with robust error variance [Zou 2004]. The explanatory variables in the model will include study vaccine group. The dependent variable will be the incidence rate of the endpoint of interest. The robust error variances will be estimated using the repeated statement and the participant identifier. The Poisson distribution will be used with a logarithm link function. The site (depending on the distribution of endpoints) and the age strata will be included in the model as covariates. To assess incidence rates rather than absolute counts of cases, accounting for differences in follow-up times starting with 7 days after the second vaccination among participants, an offset will be utilized in the Poisson regression. In case the total number of events to be analysed may be too low for an asymptotic method proposed (i.e., ≤ 5 events in either treatment group), an alternative method based on the single sample exact binomial distribution may be used for the analysis. This method is based on the proportion of the events in the SARS-CoV-2 rS with Matrix-M1 adjuvant group among the total number of events observed in both treatment groups after

SARS-CoV-2 rS Vaccine Novavax, Inc.

adjusting for the differential number of subjects (or inclusive of differential lengths of follow-up) between the 2 treatment groups.

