Hypothesis testing of the primary efficacy endpoint will be carried out against H0: VE \leq 30%. Rejection of the null hypothesis, H0: VE \leq 30% demonstrates a statistically significant vaccine effect (i.e., alpha-adjusted lower bound confidence interval [LBCI] > 30%) will be considered meeting the prespecified study success criterion. The study will also continue for the intended duration to measure efficacy, immunogenicity, and safety endpoints, regardless of primary endpoint success at the interim analyses or the final efficacy analysis. The final formal analysis of the primary efficacy endpoint will be triggered when approximately 152 PP-EFF participants with symptomatic mild, moderate, or severe COVID-19 endpoints have accrued. Also, in order to be able to respond to the unexpected and rapidly evolving COVID-19 pandemic situation globally, other factors such as requests by government or public health agencies may also be factored into the decision-making to unblind the study for the final analysis, but this always occurs in consultation with lead regulatory agencies.

The secondary and exploratory efficacy endpoints will be analysed using the same method as the primary efficacy analysis described above. Analysis of secondary and exploratory efficacy endpoints will be performed without adjustment for multiple comparisons (i.e., two-sided alpha of 0.05). The final interpretation of the overall vaccine efficacy will be based on the totality of statistical evidence, including immunogenicity results and the clinical importance in discussions with the regulatory agencies and scientific communities. The EOS analysis will be performed when the last participant completes the last visit (12 months after the last study vaccination) or discontinues earlier.

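### As written, the exploratory efficacy endpoint counted from Day 14 can admit no Day 14 to 28 cases or person-time, so it repeats the primary result

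*Protocol*

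**What the plan says.** Protocol Section 2.2.3, repeated in the synopsis, defines an exploratory endpoint of first PCR-confirmed symptomatic COVID-19 "with onset at least 14 days after first study vaccination (e.g., Day 14) in serologically negative" adults. The primary endpoint in Section 2.2 has the same case definition and the same baseline serostatus, but runs "with onset at least 7 days after second study vaccination (e.g., Day 28) in serologically negative" adults. The two differ only in when counting starts.

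Four other statements govern which cases and how much time can enter:

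- Section 6.2.2, and the synopsis text on nose/throat testing: "only those SARS-CoV-2 cases detected 7 days after second study vaccination will be utilised in study efficacy endpoints". No endpoint is exempted, although swabs are taken over a longer period, to confirm "the presence of SARS-CoV-2 beginning on Day 0 until the EOS".
- Section 7.3.1: the Poisson model uses an offset "accounting for differences in follow-up times starting with 7 days after the second vaccination among participants".
- Section 7.3.1: "The secondary and exploratory efficacy endpoints will be analysed using the same method as the primary efficacy analysis described above".
- Section 7.2: the PP-EFF set requires both doses. "All analyses of the PP-EFF population will also exclude any illness episodes with positive SARS-CoV-2" before 7 days after dose 2.

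Section 4.3 adds that participants with possible COVID-19 symptoms that may also be reactogenicity "within 7 days of either study vaccine dose will NOT be required to be tested for SARS-CoV-2 PCR".

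**The concern.** The only information this endpoint adds to the primary is what happens between Day 14 and 7 days after dose 2: protection after one dose, and the days around the second. The case rule and the offset both remove exactly that interval. If they are followed, the trial reports an efficacy figure labelled as starting on Day 14 that contains nothing from Days 14 to 28.

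Opening the window raises a second, smaller issue. In the week after dose 2, some possible COVID-19 symptoms need not be PCR tested. Fever, fatigue, muscle aches, headache and nausea/vomiting appear both among the qualifying symptoms (Table 2-2) and on the reactogenicity scale (Table 9-1). Section 1.3 reports greater reactogenicity after second vaccinations. If the vaccine arm has more such symptoms than the saline arm, more of its true cases could go untested, which would favour the vaccine. The primary endpoint starts after that week; a Day 14 endpoint includes it.

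**Working it through.** **Following one case through the rules.** Take a baseline-seronegative participant with onset and a positive PCR on Day 20, and dose 2 on Day 21.

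1. Section 2.2.3: Day 20 is after Day 14, so the case meets the endpoint definition.
2. Section 6.2.2: it was detected before Day 28 (21 + 7), so it may not be used in an efficacy endpoint.
3. Section 7.3.1: follow-up for the offset starts on Day 28 and a first case ends it on Day 20, giving 20 − 28 = −8 days. With a log link the offset is the log of follow-up time, which is undefined here. A participant who never receives dose 2 has no start date at all.
4. Section 7.2: if PP-EFF is used, the episode is removed again.

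Section 6.2.2 is worded by detection and the endpoint by onset. A case with onset just before the cut and a first positive test just after it would therefore pass step 2, but it still fails step 3. Steps 2 and 3 apply equally to the ITT set, so changing the set alone does not restore the endpoint. Cases usable from Days 14 to 28: 0.

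**Size.** The protocol gives no expected count for this endpoint. Inputs: 15,000 randomised 1:1 and 90% evaluable (Section 7.1), so 7,500 × 0.90 = 6,750 per arm; annual incidence 1% to 5% (Section 3), assumed constant and applied to placebo; dose 2 on Day 21, so the window is 14 days.

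- Placebo cases = 6,750 × incidence × 14/365. At 1%: 2.6. At 5%: 12.9.
- If dose 2 is given on Day 28, the end of its window, 21 days are lost: 6,750 × incidence × 21/365 = 3.9 to 19.4 placebo cases.
- Both arms over 14 days = placebo cases × (2 − VE). At VE 60% in the window: 3.6 to 18.1. At VE 0%: 5.2 to 25.9.
- Days 14 to 21 alone, which the post-dose-2 testing rule does not touch: half of these, 1.8 to 12.9.

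**Share of all cases from Day 14.** At VE 60% primary cases accrue at 6,750 × incidence/365 × 1.4 per day, so 152 cases take about 587 days of follow-up at 1% and 117 days at 5%. The window's share is 14/(14 + 587) = 2% to 14/(14 + 117) = 11%.

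**Effect on the estimate (illustration).** At VE 60%, 152 cases split as 152/1.4 = 108.57 placebo and 43.43 vaccine. Suppose VE in the window were 0%, adding equal cases to each arm:

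- 1% incidence: 1 − (43.43 + 2.59)/(108.57 + 2.59) = 58.6%.
- 5% incidence: 1 − (43.43 + 12.94)/(108.57 + 12.94) = 53.6%.

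As written, the Day 14 figure would still read 60%.

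**Primary analysis.** With looks at 66, 110 and 152 events and the Table 7-2 nominal alphas, simulated overall power at VE 60% is 89.8%, against 90% stated. Nothing in this point changes that.

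**The case against.** The best defence is that an endpoint's own definition should prevail over a general sentence in the procedures section. Section 2.2.3 also lists N-protein seroconversion counted from baseline, which suggests the Day 28 wording was not meant to govern every endpoint. Section 7.3 leaves analysis detail to the SAP, which is not at hand and may resolve the matter. This shows what was probably intended. It does not remove the conflict, because the case rule and the offset start are stated in the protocol without exception.

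Three stronger readings are tempting, and the protocol does not support them:

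- *That the endpoint cannot be measured.* Swabbing and case ascertainment run from Day 0 (Section 6.2.2, Table 3-1). The data will exist.
- *That testing is waived outright in Days 21 to 28.* Section 4.3 covers only symptoms that may be reactogenicity, and says testing is not required rather than not allowed. Cough, loss of taste or smell, and sore throat with congestion and runny nose are in Table 2-2 but not in Table 9-1. The period follows the actual dose 2 date, so it can reach Day 35.
- *That the protocol assigns this endpoint to PP-EFF.* Section 7.3.1 carries over the method and names PP-EFF for the primary endpoint. Several secondary endpoints are regardless of baseline serostatus (Section 2.2.2.2) and cannot be run in a seronegative-only set, so the same method cannot always mean the same set.

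It is also fair that the reactogenicity statement comes from a Phase 1 study of 131 healthy adults aged 18 to 59, and that the size of any testing bias cannot be calculated from the protocol.

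**Conclusion.** The concern holds as a contradiction in the counting rules. Taken together, the case rule in Section 6.2.2 and the synopsis and the offset in Section 7.3.1 admit no case or person-time from Days 14 to 28, so the exploratory endpoint returns the primary result under a different label. Use of PP-EFF would remove the same episodes a second time, but the conclusion does not depend on it.

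About 2.6 to 12.9 placebo cases are at issue, assuming constant 1% to 5% annual incidence, 6,750 evaluable per arm and dose 2 on schedule. The fall in VE to between 58.6% and 53.6% further assumes no protection in the window and is an illustration only. A reader might infer that the trial's main conclusion is at risk. It is not: one exploratory endpoint is affected, and the primary analysis, its power and its alpha stand.

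**What to change.** 1. In Section 6.2.2 and the matching synopsis text, limit the case rule to endpoints counted from 7 days after dose 2. Limit the Day 28 episode exclusion in Section 7.2 in the same way.
2. For the Day 14 endpoint, name a baseline-seronegative set with no positive test before Day 14, and say whether receipt of dose 2 is required. That is a choice of question for the sponsor. Requiring dose 2 would drop anyone who falls ill after Day 14 and then does not receive it.
3. In Section 7.3.1, start the offset for this endpoint at Day 14.
4. Keep the endpoint definition as it is, and add a sensitivity analysis that leaves out events and person-time in the 7 days after the actual dose 2 date in both arms. Removing that week from the main analysis would change the definition and discard cases that were properly tested.

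The cost is wording in Sections 6.2.2, 7.2 and 7.3.1 and the synopsis, plus one analysis set and one sensitivity analysis from data already collected. The sensitivity analysis gives up a week of events. The changes should be made before unblinding, because deciding afterwards which early cases count would be post hoc.
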